#### 9.1 Haemophilia Symptom Questionnaire (Haemo-Sym)

The hemophilia symptom questionnaire (Haemo-Sym) is a self reported instrument of measuring symptom severity in patients with hemophilia and has two subscales: pain and bleeds.

Information on the Haemo-Sym is to be obtained from electronic patient diaries.

The questions in the Haemo-Sym questionnaire are to be assigned to the subscales of pain and bleeds as set out in Table 1:

Table 1 Haemo-Sym Questionnaire Subscales

Question (Severity of)	Subscale
Spontaneous bleeding in my joints (unrelated to injury or activity)	Bleed
Spontaneous bleeding in my muscles (unrelated to injury or activity)	Bleed
Prolonged bleeding after injury in spite of treatment	Bleed
Intense pain because of bleeding event	Bleed
Pain because of swelling in my joints	Pain
Joint pain due to active bleed	Bleed
Bleeding during personal hygiene routine (during shaving, tooth	Bleed
brushing or flossing)	
Pain because of climbing stairs	Pain
Pain upon waking in the morning	Pain
Constant pain	Pain
Pain because of active arthritis	Pain
Pain in my muscles	Pain
Pain that needs medication	Pain
Joint sensitivity to weather conditions	Pain
Reduced range of joint movement	Pain
Joint deformity	Pain
Sleep disturbance because of pain or bleeds	Pain
Blood in my urine	None
Nose bleeds	None

Results are to be assigned scores as follows:

- Absent = 0.
- Very mild = 1.
- Mild = 2.
- Moderate = 3.
- Severe = 4.
- Very severe = 5.

The score for each subscale is determined only if at least 50% of the results in that subscale is available. The score is to be determined as:

$$Score = \frac{MeanScore}{5} * 100$$

where MeanScore is the mean of the available results in the particular subscale. If less than 50% of the results in a subscale is available then no score is to be calculated for that subscale.

The total score for the Haemo-Sym questionnaire is then to be determined as the mean score of the two subscales should both subscale scores be available.

The Haemo-Sym scores and changes from baseline are to be summarized for the FAS by treatment regimen and age category. The number and proportions of subjects with an improvement (defined as a decrease in Haemo-Sym score of greater than 1) is to be presented for the FAS. A Wilcoxon Signed-Rank test for paired samples is to be presented on the FAS comparing the baseline and study completion scores for any statistical significant differences. The following SAS® code is to be used to perform the Wilcoxon Signed-Rank test for paired samples:

```
PROC UNIVARIATE DATA = <ds>;
   VAR <Change>;
   ODS OUTPUT TestsForLocation=<outds> (WHERE = 'test = 'signed Rank'));
RUN;
QUIT;
```

where <ds> refers to the input dataset, <Change> the change from baseline at the completion visit and <outds> the resulting dataset from the procedure.

Statistical significant differences are present between baseline and completion results if a p-value of <0.05 is obtained.

Haemo-Sym individual results and calculated scores are to be listed for the FAS.

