10.5.2 Patient Reported Outcomes

The following PROs will be assessed at the start of prophylaxis treatment, every 6 months and at the end of study visit:

- Bleed and pain severity will be measured using the Haemo-SYM for subjects ≥ 18 years of age
- HRQoL will be assessed using the Short Form 36 (SF-36) for subjects ≥ 14 years of age
- HRQoL will be assessed using the Pediatric Quality of Life Inventory™ (PedsQL^{xiii}) for subjects < 14 years of age (for subjects aged ≥ 8 to < 14 years, the PedsQL Child report (23 items) will be completed; for subjects aged ≥ 5 to < 8 years, the PedsQL Parent report (23 items) will be completed; for subjects aged ≥ 2 and < 5 years, the PedsQL Parent report (21 items) will be completed; for subjects aged < 2 years, the PedsQL is not used)
- Patient satisfaction with treatment will be assessed using the Satisfaction Questionnaire (for subjects aged ≥ 12 years, the subject completes the questionnaire; for subjects aged < 12 years, the caregiver completes it on behalf of the subject)
- Patient Activity Level (for subjects aged ≥ 12 years, the subject completes the assessment; for subjects aged < 12 years, the caregiver completes it on behalf of the subject)

xiiiNOTE: Patients should be given the same questionnaire at follow-up that they were given at baseline, even if they move up an age range during the study.

Details on each of the PROs are as follows:

- **Haemo-SYM Questionnaire** – This is a self-administered, validated questionnaire designed to assess symptom severity in patients with hemophilia. This measure contains 17 items and includes 2 domains: Bleeds and Pain. Scores for each of these 2 domains can be calculated, with higher scores indicating more severe symptoms.
- **SF-36** – The SF-36 is a self-administered, validated questionnaire designed to measure generic HRQoL. This 36-item questionnaire measures 8 domains, including: Physical functioning, Role-physical, Bodily pain, General health, Vitality, Social functioning, Role emotional, and Mental health. Two summary scores can be calculated, the Physical Component Score, and the Mental Component Score. Additionally, scores can be calculated for each of the 8 domains. Higher scores indicate better health status.

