13.4.5 Patient Reported Outcomes

13.4.5.1 Haemo-SYM

Bleed and pain severity will be measured using the Haemo-SYM questionnaire with higher scores on the Haemo-SYM indicating more severe symptoms. Changes from baseline in the Haemo-SYM scores will be tested for statistical significance using a Wilcoxon test for paired samples. Number and proportion of subjects with an improvement in the Haemo-SYM pain subscale will be tabulated.

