After the z-scores have been determined, the z-scores are to be used to determine norm-based scores that are to be presented in listings and summaries. The norm based scores are to be determined as:

$$XX_N = 50 + (XX_z \times 10)$$

where XX represents the different domains (PF, RP, BP, GH, VT, SF, RE and MH).

The raw aggregate summary scores for the physical and mental components are to be determined as follows:

- $AGG_{Phys} = (PF_z \times 0.42402) + (RP_z \times 0.35119) + (BP_z \times 0.31754) + (GH_z \times 0.24954) + (VT_z \times 0.02877) + (SF_z \times (-0.00753)) + (RE_z \times (-0.19206)) + (MH_z \times (-0.22069))$
- $AGG_{Ment} = (PF_z \times (-0.22999)) + (RP_z \times (-0.12329)) + (BP_z \times (-0.09731)) + (GH_z \times (-0.01571)) + (VT_z \times 0.23534) + (SF_z \times 0.26876) + (RE_z \times 0.43407) + (MH_z \times 0.48581)$

The normalized aggregate scores that are to be presented in listings and summaries are determined as:

$$YY_N = 50 + (AGG_{YY} * 10)$$

where YY is either the physical component score or mental component score.

Any domain with less than half of the questions answered will have no score calculated. For scales with any questions not answered, but with more than half of the questions answered, the raw scale is to be adjusted in terms of the lowest and highest possible score, including the possible raw range. All other scores are to be affected by this change in transformed score. As an example, say question 3a is not answered, then the lowest score for physical functioning is to change from 10 to 9, the highest score is to change from 30 to 27 and the possible raw range from 20 to 18. The new values are to be used in determining the transformed score for physical functioning.

The SF-36 scores and changes from baseline are to be summarized for the FAS by treatment regimen and age category. The number of subjects with an improvement (defined as an increase in SF-36 score greater than 1) are to be presented for the FAS. A Wilcoxon Signed-Rank test for paired samples is to be presented on the FAS comparing the baseline and study completion scores for any statistical significant differences using the SAS code provided in Section 9.1: Haemophilia Symptom Questionnaire (Haemo-Sym).

SF-36 individual results and calculated scores are to be listed for the FAS.

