		Keeping up with	I have trouble
		school activities	keeping up with my
			school work
		Missing school	I miss school
		because of not	because of not
		feeling well	feeling well
		Missing school to	I miss school to go
		go to the doctor or	to the doctor or
		hospital	hospital

Each question of the PedsQL is to be scored as follows:

Never: 100

Almost never: 75Sometimes: 50

• Often: 25

Almost always: 0

Scores for the categories of physical functioning, emotional functioning, social functioning and school functioning are to be derived as the mean of the individual question scores of available data. Missing data are not to be imputed. At least half of the questions in a particular score category needs to be answered for a score to be presented.

The psychosocial health summary score is to be derived as the mean of the individual questions for the emotional functioning, social functioning and school functioning categories. The physical health summary score is to be set equal to the physical functioning category score.

The PedsQL scores and changes from baseline are to be summarized for the FAS by treatment regimen and age category. The number of subjects with an improvement (defined as an increase in PedsQL score greater than 1) are to be presented for the FAS. A Wilcoxon test for paired samples is to be presented on the FAS comparing the baseline and study completion scores for any statistical significant differences using the SAS code provided in Section 9.1: Haemophilia Symptom Questionnaire (Haemo-Sym).

PedsQL individual results and calculated scores are to be listed for the FAS.

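### The one-point rule for PRO improvement in SAP 9.1 to 9.3 is met by one item moving one category on nearly every subscale, and only improved subjects are counted

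*SAP*

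**What the plan says.** The three PRO sections of the SAP share one numerical rule. SAP 9.1 presents the number and proportion of subjects with an "improvement (defined as a decrease in Haemo-Sym score of greater than 1". SAP 9.2 counts subjects with an "improvement (defined as an increase in SF-36 score greater than 1", and SAP 9.3 counts those with an "improvement (defined as an increase in PedsQL score greater than 1". None of the sections gives a reason for the value 1, a measurement-error figure or a responder threshold.

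The protocol is the source of the count but sets no size for it. Protocol 13.4.5.1 states: "Number and proportion of subjects with an improvement in the Haemo-SYM pain subscale will be tabulated". Protocol 13.4.5.2 and 13.4.5.3 plan the same for SF-36 and PedsQL. SAP 9.1 does not say whether its rule applies to the pain subscale, the bleed subscale or the total.

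Neither document plans a count of worsened or unchanged subjects. The SAP does plan summaries of scores and of changes from baseline, a signed-rank test of baseline against completion, and listings of individual scores.

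**The concern.** A cut-off for improvement is useful if it separates a change worth reporting from the ordinary variation in how a person answers the same questionnaire twice. A fixed value of 1 can do that only if the score can move by less than 1. If the smallest ordinary movement already exceeds 1, the rule amounts to any net movement in the favourable direction.

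That matters more here because the study is open-label with no control group (Protocol synopsis and 8.5). No comparison arm shows how many subjects would cross the line through response noise, and no worsened row shows the movement the other way. A reader who sees only a percentage improved cannot tell a real shift from equal numbers moving up and down. The percentage is easy to quote on its own, and PROs are a secondary objective (Protocol 7.3.1, SAP 1.1.2.1).

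**Working it through.** The documents state no responder rate, so there is no figure of theirs to reproduce. The check has two parts.

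**1. Change in score when one item moves one category (exact, all items answered)**

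*Haemo-Sym.* Items score 0 to 5. The subscale is the mean divided by 5, times 100, "where MeanScore is the mean of the available results in the particular subscale". SAP Table 1 assigns 11 items to Pain and 6 to Bleed, which agrees with the 17 items in Protocol 10.5.2. With k items the step is 100/(5k).
- Pain: 100/55 = 1.82
- Bleed: 100/30 = 3.33
- Total (mean of the two subscales): 1.82/2 = 0.91 through a pain item, 3.33/2 = 1.67 through a bleed item

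*SF-36.* The reported metric is norm-based (50 + 10z), so the step is (raw step / raw range) × 100 / SD × 10, with the constants in SAP 9.2.
- General Health, smallest step (5 to 4.4): 0.6/20 × 100/20.97821 × 10 = 1.43
- Physical Functioning: 1/20 × 100/23.75883 × 10 = 2.10
- Role-Emotional: 1/12 × 100/21.43778 × 10 = 3.89
- By the same formula, smallest steps: Role-Physical 2.45, Bodily Pain 2.54, Mental Health 2.82, Vitality 3.12
- Social Functioning: its constants are not legible in the text available. The 0-100 step is 1/8 × 100 = 12.5, so the SD would have to be at least 125 for the norm-based step to be 1 or less.
- Component scores are mixed. Physical: 2.10 × 0.42402 = 0.89 through Physical Functioning. Mental: 3.12 × 0.23534 = 0.73 through Vitality, but 3.89 × 0.43407 = 1.69 through Role-Emotional.

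*PedsQL.* Items move in steps of 25 and are averaged, so the step is 25/k.
- Physical (8 items): 3.13
- Emotional, social, school (5 items each): 5.0
- Nursery (3 items): 8.33
- Psychosocial (15 items): 1.67
- A 23-item mean: 1.09, if that is how the total is formed; SAP 9.3 does not define it.

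Unanswered items reduce the denominator and make the subscale steps larger. One qualification applies to SF-36: General Health and Bodily Pain contain unevenly spaced items, so offsetting moves can leave a net change below 1. For General Health, a net raw change of 0.4 gives 0.4/20 × 100/20.97821 × 10 = 0.95.

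**2. Share counted as improved with no true change (assumption-based)**

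Assume each item independently moves one category up with probability p, down with probability p, and otherwise stays. On an equal-step subscale where one step exceeds 1, the share improved is the probability of a net favourable sum. For 2 items this is p² + 2p(1 − 2p): 0.0025 + 0.09 = 9.3% at p = 5%, and 0.04 + 0.24 = 28% at p = 20%. Longer scales follow by convolution.

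| Score | p = 5% per direction | p = 20% per direction |
|---|---|---|
| 2-item domain | 9% | 28% |
| 3-item domain | 13% | 32% |
| Bleed (6 items) | 21% | 37% |
| Pain (11 items) | 29% | 41% |
| 23-item score | 36% | 43% |

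The model is symmetric, so the same share worsens.

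If 40% of subjects have the best possible score at both visits (also an assumption), multiply by 0.6. Pain becomes 0.6 × 28.7% = 17% to 0.6 × 40.5% = 24%, and Bleed becomes 0.6 × 20.9% = 13% to 0.6 × 37.2% = 22%.

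**The case against.** The strongest reply is that the SAP does what the protocol asks. Protocol 13.4.5 promises a count of subjects with an improvement and sets no minimum size, so a rule that amounts to any net improvement carries that out. The count has no test or success criterion attached. The PRO outcome is change from baseline, and that is handled properly: SAP 5.8 gives quartiles, median, minimum and maximum and makes tests two-sided, and individual scores are listed. The table layouts sit in Output Templates that are not available here.

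Most of this stands. There is no contradiction between the documents, and the main PRO analyses do not depend on the rule. Two stronger readings therefore fail.
- A reader might infer that worsening is hidden, or that the PRO objective cannot be met. The change summaries, signed-rank tests and listings show worsening; only a count beside the improved percentage is absent.
- A reader might infer that a fixed share, say 20-45%, would be falsely counted as improved. The scoring does not imply that. The share depends on item instability, which the documents do not give; it falls below 20% on short domains and never exceeds 43.4% under the model above. Subjects already at the best score lower it further.

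The reply does not supply a reason for the value 1. A numerical cut-off suggests that small changes have been screened out, and on most of these subscales none are.

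**Conclusion.** The point holds as a modest one. It follows exactly from the SAP's scoring that one item moving one category exceeds the cut-off on both Haemo-Sym subscales, on every SF-36 domain with legible constants and on every PedsQL domain. The rule has some effect only on the Haemo-Sym total, on some SF-36 component-score steps, and on offsetting moves within two SF-36 domains.

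Because only improved subjects are counted in an uncontrolled study, the percentage by itself cannot be told apart from symmetric response noise. How large that noise would be is an assumption. It is about 9-28% for a 2-item domain up to 36-43% for a 23-item score if items move independently 5% to 20% per direction, and lower with many subjects at the best score.

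The consequence is confined to a descriptive secondary table. The change summaries and signed-rank tests are unaffected.

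**What to change.** In SAP 9.1 to 9.3:
- Name the score that the count uses. For Haemo-Sym this is the pain subscale, as Protocol 13.4.5.1 states.
- Tabulate improved, unchanged and worsened, with the same cut-off in both directions.
- Replace 1 with a threshold larger than a single-item step on the named score, fixed before database lock. Use the instrument's validated responder threshold if the sponsor holds one; otherwise use a stated distribution-based value, described as a convention.
- If the one-point rule is kept, label the row as any net improvement.

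The cost is SAP wording and two more rows per table, with no new data or visits. The downside for the sponsor is a less favourable-looking result: a larger threshold gives a smaller improved percentage, shown next to a worsened one.

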## 9.2 Short-Form 36 (SF-36) Questionnaire

The Short-Form 36 (SF-36) is a self-administered, validated questionnaire designed to measure general health related quality of life. The questionnaire is divided in eight domains including: physical functioning, role-physical, bodily pain, general health, vitality, social functioning, role emotional and mental health. From this questionnaire two summary scores can be calculated, the physical component score and the mental component score.

Information on the SF-36 is to be obtained from electronic patient diaries.

The questions in the SF-36 are assigned to domains and scored as set out in Table 2.

Table 2 SF-36 Scoring for Individual Questions

Question	Domain	Score
1. In general, would you say your health is:	General Health	Excellent: 5
	(GH)	Very Good: 4.4
		Good: 3.4
		Fair: 2
		Poor: 1
2. Compared to one year ago, how would	No Scale	Much better now than one year ago: 1
you rate your health in general now?		Somewhat better now than one year ago: 2
		About the same as one year ago: 3
		Somewhat worse now than one year ago: 4
		Much worse now than one year ago: 5
3. The following questions are about activities	you might do during a typ	
activities? If so, how much?	,	,,,,,
3a. Vigorous activities	Physical	Yes, limited a lot: 1
	Functioning (PF)	Yes, limited a little: 2
	8 (-1)	No, not limited at all: 3
3b. Moderate activities	Physical	Yes, limited a lot: 1
	Functioning (PF)	Yes, limited a little: 2
	1 meneralis (11)	No, not limited at all: 3
3c. Lifting or carrying groceries	Physical	Yes, limited a lot: 1
Sc. Enting of carrying groceries	Functioning (PF)	Yes, limited a little: 2
	Tunctioning (11)	No, not limited at all: 3
3d. Climbing several flight of stairs	Physical	Yes, limited at all. 3
3d. Climbing several fight of stans	Functioning (PF)	Yes, limited a little: 2
	runctioning (FF)	No, not limited at all: 3
2- Climbin Right of string	Physical	Yes, limited a lot: 1
3e. Climbing one flight of stairs	A CONTRACTOR OF STREET	
	Functioning (PF)	Yes, limited a little: 2
20 D 1: 1 1:	Di : 1	No, not limited at all: 3
3f. Bending, kneeling or stooping	Physical	Yes, limited a lot: 1
	Functioning (PF)	Yes, limited a little: 2
2 777 11 7	The same and a	No, not limited at all: 3
3g. Walking more than a mile	Physical	Yes, limited a lot: 1
	Functioning (PF)	Yes, limited a little: 2
	7	No, not limited at all: 3
3h. Walking several hundred yards	Physical	Yes, limited a lot: 1
	Functioning (PF)	Yes, limited a little: 2
		No, not limited at all: 3
3i. Walking one hundred yards	Physical	Yes, limited a lot: 1
	Functioning (PF)	Yes, limited a little: 2
		No, not limited at all: 3
3j. Bathing or dressing yourself	Physical Physical	Yes, limited a lot: 1
	Functioning (PF)	Yes, limited a little: 2
		No, not limited at all: 3
		ne following problems with your work or other
regular daily activities as a result of your phys		Taw as a second
4a. Cut down on the amount of time you	Role-Physical (RP)	All of the time: 1
spent on work or other activities		Most of the time: 2
		Some of the time: 3
		A little of the time: 4
	8	None of the time: 5
4b. Accomplished less than you would like	Role-Physical (RP)	All of the time: 1
	100 522 253	Most of the time: 2
		Some of the time: 3
		A little of the time: 4
	1	None of the time: 5

Question	Domain	Score
4c. Were limited in the kind of work or	Role-Physical (RP)	All of the time: 1
other activities	2 3 2	Most of the time: 2
		Some of the time: 3
		A little of the time: 4
		None of the time: 5
4d. Had difficulty performing the work or	Role-Physical (RP)	All of the time: 1
other activities (for example, it took extra		Most of the time: 2
effort)		Some of the time: 3
		A little of the time: 4
		None of the time: 5
5. During the past 4 weeks, how much of the ti	me have you had any of the	e following problems with your work or other
regular daily activities as a result of any emotion	onal problems (such as feel	ing depressed or anxious)?
5a. Cut down on the amount of time you	Role-Emotional	All of the time: 1
spent on work or other activities.	(RE)	Most of the time: 2
	0.50.53.50	Some of the time: 3
		A little of the time: 4
		None of the time: 5
5b. Accomplished less than you would like	Role-Emotional	All of the time: 1
The state of the s	(RE)	Most of the time: 2
	80 850	Some of the time: 3
		A little of the time: 4
		None of the time: 5
5c Did work or other activities less	Role-Emotional	All of the time: 1
carefully than usual	(RE)	Most of the time: 2
•	· - /	Some of the time: 3
		A little of the time: 4
		None of the time: 5
6. During the past 4 weeks, to what extent	Social Functioning	Not at all: 5
has your physical health or emotional	(SF)	Slightly: 4
problems interfered with your normal		Moderately: 3
social activities with family, friends,		Quite a bit: 2
neighbours or groups?		Extremely: 1
7. How much bodily pain have you had	Bodily Pain (BP)	None: 6
during the past 4 weeks?		Very mild: 5.4
P		Mild: 4.2
		Moderate: 3.1
		Severe: 2.2
		Very severe: 1
8. During the past 4 weeks, how much did	Bodily Pain (BP)	If Question 7 Answered:
pain interfere with your normal work		Not at all (and Question 7 = None): 6
(including both work outside the home and		Not at all (and Question 7 not None): 5
housework)?		A little bit: 4
		Moderately: 3
		Quite a bit: 2
		Extremely: 1
		2
		If Question 7 Not Answered:
		Not at all: 6
		A little bit: 4.75
		Moderately: 3.5
		Quite a bit: 2.25
		Extremely: 1
9 These questions are about how you feel and	how things have been with	you during the past 4 weeks. For each question,
		eeling. How much of the time during the past 4
weeks	journate cooli it	pure sum outing the past 1
9a. Did you feel full of life?	Vitality (VT)	All of the time: 5
a. 2.5 jour real roll of life:	( * 1)	Most of the time: 4
		Some of the time: 3
		A little of the time: 2
		None of the time: 1
Oh Have very become 2	Montal II14	All of the time: 1
9b. Have you been very nervous?	Mental Health	
	(MH)	Most of the time: 2
		Some of the time: 3
		A little of the time: 4
	1	None of the time: 5

Question	Domain	Score
9c. Have you felt so down in the dumps	Mental Health	All of the time: 1
that nothing could cheer you up?	(MH)	Most of the time: 2
		Some of the time: 3
		A little of the time: 4
		None of the time: 5
9d. Have you felt calm and peaceful?	Mental Health	All of the time: 5
P	(MH)	Most of the time: 4
	()	Some of the time: 3
		A little of the time: 2
		None of the time: 1
9e. Did you have a lot of energy?	Vitality (VT)	All of the time: 5
Jes Zab you mare a far of thingy.		Most of the time: 4
		Some of the time: 3
		A little of the time: 2
		None of the time: 1
9f. Have you felt downhearted and	Mental Health	All of the time: 1
depressed?	(MH)	Most of the time: 2
depressed.	(1.111)	Some of the time: 3
		A little of the time: 4
		None of the time: 5
9g. Did you feel worn out?	Vitality (VT)	All of the time: 1
og. Did you leef worll out!	Vitality (VI)	Most of the time: 2
		Some of the time: 3
		A little of the time: 4
		None of the time: 5
9h. Have you been happy?	Mental Health	All of the time: 5
9n. Have you been happy?	HISTORIAN CONTRACTOR OF THE PROPERTY OF THE PR	Most of the time: 4
	(MH)	Some of the time: 3
		A little of the time: 2
		None of the time: 1
0: D:1	Tr. 1: ATT	All of the time: 1
9i. Did you feel tired?	Vitality (VT)	Most of the time: 1 Most of the time: 2
		Some of the time: 3
		A little of the time: 4
10 D : 1 11 1 C	C IIF C	None of the time: 5
10. During the past 4 weeks how much of	Social Functioning	All of the time: 1
the time has your physical health or	(SF)	Most of the time: 2
emotional problems interfered with your		Some of the time: 3
social activities (like visiting fiends,		A little of the time: 4
relatives etc.)?		None of the time: 5
11. How true or false is each of the following st		T 7
11a. I seem to get sick a little easier than	General Health	Definitely true: 1
other people	(GH)	Mostly true: 2
		Don't know: 3
		Mostly false: 4
		Definitely false: 5
11b. I am as healthy as anybody I know	General Health	Definitely true: 5
	(GH)	Mostly true: 4
		Don't know: 3
		Mostly false: 2
		Definitely false: 1
11c. I expect my health to get worse	General Health	Definitely true: 1
	(GH)	Mostly true: 2
	C1 100	Don't know: 3
		Mostly false: 4
		Definitely false: 5
11d. My health is excellent	General Health	Definitely true: 5
Contraction and the Contract of the State of Contraction of Contrac	(GH)	Mostly true: 4
		Don't know: 3
		Mostly false: 2
		Definitely false: 1

After scores have been assigned as in Table 2, raw scores for each domain are to be calculated as set out in Table 3.

Domain	Items to Sum	Lowest and Highest Possible Score	Possible Raw Score Range
Physical Functioning (PF)	3a + 3b + 3c + 3d + 3e + 3f + $3g + 3h + 3i + 3j$	10, 30	20
Role-Physical (RP)	4a + 4b + 4c + 4d	4, 20	16
Bodily Pain (BP)	7+8	2, 12	10
General Health (GH)	1 + 11a + 11b + 11c + 11d	5, 25	20
Vitality (VT)	9a + 9e + 9g + 9i	4, 20	16
Social Functioning (SF)	6+10	2, 10	8
Role-Emotional (RE)	5a + 5b + 5c	3, 15	12
Mental Health (MH)	9b + 9c + 9d + 9f + 9h	5, 25	20

Table 3 SF-36 Scoring for Domains

The score for each domain is then to be transformed to a 0-100 range using the following formula:

$$Transf.Domain = \frac{[(Actual\ Raw\ Score - Lowest\ Possible\ Raw\ Score)]}{Possible\ Raw\ Score\ Range} \times 100$$

A z-score standardization of the SF-36 transformed domain scores is to be determined as follows:

• 
$$PF_z = \frac{PF - 83.29094}{23.75883}$$
  
•  $RP_z = \frac{RP - 82.50964}{25.52028}$ 

$$P_z = \frac{RP - 82.50964}{25.52028}$$

• 
$$BP_z = \frac{BP - 71.32527}{23.66224}$$

$$BP_{z} = \frac{25.52028}{23.66224}$$

$$GH_{z} = \frac{GH - 70.84570}{20.97821}$$

$$VT_{z} = \frac{VT - 58.31411}{20.01923}$$

$$VT_z = \frac{VT - 58.31411}{20.01923}$$

• 
$$RE_z = \frac{RE - 87.39733}{21.43778}$$
  
•  $MH_z = \frac{MH - 74.98685}{17.75604}$ 

$$MH_Z = \frac{MH - 74.98685}{17.75604}$$

After the z-scores have been determined, the z-scores are to be used to determine norm-based scores that are to be presented in listings and summaries. The norm based scores are to be determined as:

$$XX_N = 50 + (XX_z \times 10)$$

where XX represents the different domains (PF, RP, BP, GH, VT, SF, RE and MH).

The raw aggregate summary scores for the physical and mental components are to be determined as follows:

- $AGG_{Phys} = (PF_z \times 0.42402) + (RP_z \times 0.35119) + (BP_z \times 0.31754) + (GH_z \times 0.24954) + (VT_z \times 0.02877) + (SF_z \times (-0.00753)) + (RE_z \times (-0.19206)) + (MH_z \times (-0.22069))$
- $AGG_{Ment} = (PF_z \times (-0.22999)) + (RP_z \times (-0.12329)) + (BP_z \times (-0.09731)) + (GH_z \times (-0.01571)) + (VT_z \times 0.23534) + (SF_z \times 0.26876) + (RE_z \times 0.43407) + (MH_z \times 0.48581)$

The normalized aggregate scores that are to be presented in listings and summaries are determined as:

$$YY_N = 50 + (AGG_{YY} * 10)$$

where YY is either the physical component score or mental component score.

Any domain with less than half of the questions answered will have no score calculated. For scales with any questions not answered, but with more than half of the questions answered, the raw scale is to be adjusted in terms of the lowest and highest possible score, including the possible raw range. All other scores are to be affected by this change in transformed score. As an example, say question 3a is not answered, then the lowest score for physical functioning is to change from 10 to 9, the highest score is to change from 30 to 27 and the possible raw range from 20 to 18. The new values are to be used in determining the transformed score for physical functioning.

The SF-36 scores and changes from baseline are to be summarized for the FAS by treatment regimen and age category. The number of subjects with an improvement (defined as an increase in SF-36 score greater than 1) are to be presented for the FAS. A Wilcoxon Signed-Rank test for paired samples is to be presented on the FAS comparing the baseline and study completion scores for any statistical significant differences using the SAS code provided in Section 9.1: Haemophilia Symptom Questionnaire (Haemo-Sym).

SF-36 individual results and calculated scores are to be listed for the FAS.

